**Page 1:**

*The following text is to be deleted:*

**VERSION NUMBER:** 1.0

**DATE:** 30 March 2017

*The following text is to be added:*

**VERSION NUMBER:** 2.0

**DATE:**  
9 June 2017

**PROTOCOL AMENDMENT NUMBER 2 (Version 2.0 to Version 3.0):****Reason for Amendment - 2: Administrative amendment**

Update to include requirements of ICH E6R2, quality management, risk-based approach and definition of critical data.

A requirement to remove the requirement for patients to be high-risk Neuroblastoma, as some patients with intermediate risk may be eligible.

Section 3.5 to clarify that oncology history may be diagnosis only and treatment only needs to include treatment in the last month.

Section 4.6 clarification of food to be given with food and the removal of standardised meals

Small administrative edits.

**Page 1:**

*The following text is to be **deleted**:*

**VERSION NUMBER:** 2.0

**DATE:** 9 June 2017

*The following text is to be **added**:*

**VERSION NUMBER:** 3.0

**DATE:** 28 Sept 2017

**Page 19:**

*The following text in italics is to be **added**:*

- Oncology history (*diagnosis*) and treatment (*over the last month*) to include concomitant medication for their indication (i.e. confirmation of eligibility for 13-CRA treatment and current treatment).

**Page 21:**

*The following text is to be **deleted**:*

appropriate standardised meals/drinks to be provided to patients during the period following dosing on PK days

*The following text in italics is to be **added**:*

which foods such as yogurt or ice cream can be given with the medicine

**Page 35:**

*The following text in italics is to be **added**:*

The Sponsor has implemented a quality management system to manage quality throughout all stages of the trial process, using a risk-based approach. A Study Management Plan will be developed and will include a risk analysis for identification, evaluation, control, communication, review and reporting of the risks to the safety and integrity of the patients and the scientific integrity of the trial. This risk analysis will identify processes and data that are critical to ensure human subject protection and reliability of results, this risk assessment will be reviewed as appropriate during the study.

**Page 44:**

*An error on the study schedule was corrected (medical history and concomitant medications to be collected at pre-trial visit) adverse events also added as to be collected on PK days).*

**PROTOCOL AMENDMENT NUMBER 3 (Version 3.0 to Version 4.0):****Reason for Amendment - 2: Administrative amendment, inconsistencies in blood sampling schedules**

Change in flow chart to remove pre-dosing blood sample as was intended, i.e. to reduce the number of samples taken from each child.

Small administrative edits.

**Page 1:**

*The following text is to be **deleted**:*

**VERSION NUMBER:** 3.0

**DATE:** 28 Sept 2017

*The following text is to be **added**:*

**VERSION NUMBER:** 4.0

**DATE:** 11 Oct 2017

**Page 12:**

*The following Text will be **deleted**:*

A pre-dose blood sample will be taken (2ml) and then blood will be sampled post-dose at time points selected as follows:

**Page 12:**

*The following Text will be **added**:*

Blood (2 ml) will be sampled post-dose at time points selected as follows:

**Page 21:**

*The following text is to be deleted:*

On Days 1 and 14 an initial blood sample will taken (pre-dose, at time zero).

**PROTOCOL AMENDMENT NUMBER 3 (Version 4.0 to Version 5.0):**

**Reason for Amendment - 3: Requirement from MHRA to include explicit timelines for pregnancy testing and addition of a lower limit of serum calcium prior to initiation of each cycle of 13-CRA.**

**Clarification of Name of Sponsor to be correct.**

**Addition of light protection and shaking requirements for test product.**

**Throughout document:**

Nova *Biopharma* Limited will be replaced with Nova *Laboratories* Limited

**Page 1:**

*The following text is to be deleted:*

**VERSION NUMBER:** 4.0

**DATE:** 11 Oct 2017

*The following text is to be added:*

**VERSION NUMBER:** 5.0

**DATE:** 08 Dec 2017

**Page 10, Synopsis, Inclusion criteria 5:**

*The text in underlined italics will be added:*

5. Negative pregnancy test for females of child-bearing potential no more than seven days before initiation of treatment, and sexually active patients and partners agreeing to undertake adequate contraceptive measures (see section 4.5).

**Page 11, Synopsis, Criteria prior to starting each cycle of 13-Cis-RA 5:**

*The text in underlined italics will be added:*

5. Serum calcium  $\geq 2.0\text{mmol/L}$  to  $\leq 2.9\text{mmol/L}$ .

**Page 11, Synopsis, Withdrawal criteria 1:**

*The text in underlined italics will be added:*

1. Positive pregnancy test - pregnancy testing will be undertaken *no more than seven days* before treatment commences and routinely *no more than seven days* before each course of treatment in females of childbearing potential. If a patient is found to be pregnant during the trial, the next course of treatment will not be given until the pregnancy has been discussed with the treating clinician, and the patient will be withdrawn from the trial whether or not treatment is continued.

**Page 21, Pregnancy prevention, Paragraph 1:**

*The text **in underlined italics** will be added:*

For women of childbearing potential all conditions of the Pregnancy Prevention Programme should be met (8). Patients of childbearing potential, their partners and parents must understand and accept the need for effective contraception, be informed and understand the potential consequences of pregnancy and the need to rapidly consult if there is a risk of pregnancy. Female patients of childbearing age must be provided with comprehensive information on pregnancy prevention and should be referred for contraceptive advice if appropriate. As part of the standard clinical care, female patients of childbearing potential will undergo a pregnancy test *no more than seven days* prior to the start of treatment and routinely no more than seven days before each course of treatment. Although the likelihood of pregnancy in patients receiving 13-CRA is extremely low, if a positive pregnancy test does result during the trial, the next course of treatment will not be given until the pregnancy has been discussed with the treating clinician, and the patient will be withdrawn from the trial whether or not treatment is continued

**Page 23, Section 5 Selection of Patients; Section 5.1, Inclusion criteria 5:**

*The text **in underlined italics** will be added:*

5. Negative pregnancy test for females of child-bearing potential *no more than seven days* before initiation of treatment, and sexually active patients and partners agreeing to undertake adequate contraceptive measures (see section 4.5).

**Page 11, Section 5 Selection of Patients; Section 5.2, Criteria prior to starting each cycle of 13-Cis-RA 5:**

*The text **in underlined italics** will be added:*

5. Serum calcium  $\geq 2.0 \text{ mmol/L}$  to  $\leq 2.9 \text{ mmol/L}$ .

**Page 11, Section 5 Selection of Patients; Section 5.2, Withdrawal criteria 1:**

*The text **in underlined italics** will be added:*

1. Positive pregnancy test - pregnancy testing will be undertaken *no more than seven days* before treatment commences and routinely *no more than seven days* before each course of treatment in females of childbearing potential. If a patient is found to be pregnant during the trial, the next course of treatment will not be given until the pregnancy has been discussed with the treating clinician, and the patient will be withdrawn from the trial whether or not treatment is continued.

**Page 26, Investigational Medicinal product, Packaging, Test Drug Product:**

*The following text is to be added:*

The medicinal product is photosensitive and should be protected from light and stored in the original carton at all times

Shake the bottle vigorously for at least 30 seconds before use

**Page 44, Appendix 1 Pregnancy testing Footnote 2:**

*The text **in underlined italics** will be added:*

2. Pregnancy test for females of childbearing age, *not more than 7 days* prior to starting treatment (each cycle).

WHO	World Health Organization

2 Version Control

This Statistical Analysis Plan (SAP) is based on the protocol version 5.0 dated 08 December 2017 and Case Report Form (CRF) version 2 dated 26 March 2018.

The population pharmacokinetic (PK) analysis detailed in the protocol is not within the scope of this SAP.

3 Study Rationale

13-CRA is administered during the remission phase in the treatment of high risk neuroblastoma (HRNBL) between cycles of immunotherapy and also in patients with unresectable, intermediate risk neuroblastoma with unfavourable INPC histology and in patients with relapsed and refractory disease who have not already received 13-CRA. It is administered orally, currently using the capsule form licensed for severe acne.

It is clear that many young children will not take solid medicines (tablets, capsules). Potential solutions to this issue include developing a liquid for parenteral use, a medicine to be administered by the rectal route

and a transdermal drug. While there are other potential solutions, the oral liquid preparation meets important criteria for this medicine including flexible dosing, ease of use, minimal additional risk to patient and carer and patient comfort.

The dose administered is in accordance with approved practice for 13-CRA extracted capsules. This is based on previous studies which have shown that the dose obtained from extracted capsules needs to be adjusted to 200mg/m²/day in order to achieve the same blood level as that seen for capsules that have been swallowed whole. Therefore the dose used in this trial will be 200mg/m²/day for both test and reference product. Patients with a body weight of ≤12kg will receive a dose of 160 mg/m².

The pharmacokinetics of 13-CRA liquid (test product) and extracted capsule (reference product) will be evaluated in over a two month period to allow for two cycles of treatment in a cross over design (one test treatment period and one reference treatment period). The 14-day treatment period and two week break between treatment cycles is based upon previous studies and is the standard treatment period for cycles of 13-CRA. If patients require a longer period of time between treatments then this will be acceptable within the visit windows (i.e. treatment period 2 will be within 14 +up to 7 days of completion of treatment period 1).

4 Objectives

The aim of this trial is to investigate the PK, safety, tolerability and palatability of oral liquid 13-CRA in patients aged from 0 months – < 21 years.

4.1 Primary Objective

- To determine the relative bioavailability and PK of 13-CRA administered as oral liquid and extracted capsule formulations

4.2 Secondary Objectives

- To determine the safety and tolerability
- To assess palatability and acceptability

5 Endpoints

5.1 Primary Endpoint

Primary endpoints are:

Primary parameters:

- Relative bioavailability
- Clearance (CL/F)
- Volume of distribution (V/F)

Secondary parameters:

- Time to maximum concentration (T_{max})
- Maximum plasma concentration (C_{max})
- Area under plasma concentration time curve (AUC)
- Half life ($t_{1/2}$)
- Levels of the metabolite 4-oxo-13-cis-RA

5.2 Secondary Endpoints

Safety parameters:

- Evaluate the local (oro-pharyngeal) tolerability
- Skin toxicity
- Hypercalcaemia (noted as adverse events if intervention required)
- Hepatotoxicity (noted as adverse events if intervention required)
- Triglycerides (noted as adverse events if intervention required)

Palatability and acceptability parameters:

- Evaluate the taste acceptability of the new oral formulation of 13-CRA

6 Study Design

This is an open label, randomised, multiple dose, cross-over relative bioavailability and PK trial of oral 13-CRA liquid administered to patients aged from 0- < 21 years. The decision to initiate 13-CRA therapy will be taken independently of the trial protocol. The trial will be conducted in patients who are attending the hospital for treatment for neuroblastoma requiring at least two cycles of 13-CRA. 13-CRA will be prescribed to patients according to the locally approved treatment protocols at a dose of 200mg/m²/day for both test and reference product. Oral 13-CRA is administered for neuroblastoma (NBL) (this is usually at a dose of 160mg/m²) for 14 days, every 4 weeks, for 6 months, however where the dose is extracted from capsules this dose is increased to 200mg/m². In this trial the dose of 13-CRA will be 200mg/m² as patients able to swallow the capsules will not be recruited to the trial. Patients with a body weight of ≤12kg will receive a dose of 160 mg/m². Patients who require their dose through a nasogastric tube or gastrostomy will be included in the trial, this will be recorded in the case record form.

Evaluation of the test and reference product will occur during two months of therapy.

Consent to take part in the trial will be obtained before any trial procedures are undertaken. Patients who are already receiving 13-CRA treatment will also be eligible for the trial, so long as they are able to commit to two cycles of the trial. The next planned 14-day treatment cycle will be classed as My-CRA Month 1. After consent to take part has been obtained and prior to the initiation of the next 14 day treatment patients will be randomised to receive either 13-CRA liquid (test product) or liquid extracted from capsule (reference product) in My-CRA Month 1. Randomisation will be done once eligibility has been confirmed and their next scheduled treatment visit is booked, in order that the appropriate medication can be made available for the patient's visit. Randomisation will be done centrally by Nova according to a randomisation list generated by the trial statistician, investigators will email (or telephone) Nova to receive randomisation details, this will be confirmed by email as "liquid first" or "extracted capsules first", pharmacy contacts will also be notified. After My-CRA month 1, patients will then cross over to the alternative formulation in My-

CRA Month 2. In all other treatment cycles patients will revert to standard therapy i.e. liquid extracted from capsules. The pharmacokinetics of 13-CRA will be evaluated during test and reference treatments (My-CRA Month 1 and 2).

When the patient attends hospital for initiation of 13-CRA treatment, it is anticipated that they will have a central line *in situ*. Patients will attend the clinic on Pharmacokinetic days; these will be Day 1 and Day 14 for each of the trial treatment periods. Blood samples for pharmacokinetic analysis will be taken over the course of six hours after which the patients will leave the clinic. Parents and patients will be asked if they are willing to return for an additional sample at 24-48 hours following their final dose on Day 14 of treatment.

7 Statistical Considerations

7.1 Sample Size

Up to 20 patients, both male and female, aged 0 – < 21 years of age will be recruited.

There are no power calculations in this trial. The objective of this trial is to estimate the population pharmacokinetics of 13-CRA following the administration of 13-CRA liquid (test product) and extracted capsule (reference product). From a statistical point of view, the collected plasma 13-CRA concentration data are expected to relate to a non-linear, mixed effects model involving repeated measures. The developed pharmacokinetic model will estimate the parameters of the model and their associated within- and between-patient variability.

In order to develop a robust population pharmacokinetic model (i.e. precisely estimated parameters), data from a minimum of 150 blood samples will be required. It is hoped that the required number of samples may be obtained from 12-18 patients. However, if problems are encountered in obtaining samples further patients may be included in the trial.

7.2 Randomisation

Prior to the initiation of the trial 13-CRA, patients will be randomised to receive either liquid or extracted capsule formulation in “My –CRA month 1”. The patients will then cross-over to the alternative formulation in “My-CRA month 2”. After the trial if a patient requires additional cycles of 13-CRA, the patient will revert to standard 13-CRA therapy i.e. extracted capsules according to local practice.

Randomisation will be done centrally by Nova according to a randomisation list generated by the trial statistician, investigators will email (or telephone) Nova to receive randomisation details, this will be confirmed by email as “liquid first” or “extracted capsules first”, pharmacy contacts will also be notified.

8 Major Protocol Deviations

Protocol violations are any deviations from the procedures outlined in the protocol, for example, missed evaluations, incorrect timing of evaluations, non-compliance with investigation medical product (IMP) and intake of prohibited medications. It is the investigator’s responsibility to make all reasonable efforts to avoid protocol violations in order to avoid possible exclusion of the patient from the trial and/or analyses.

Major protocol deviations are defined as those deviations from the study protocol that may have the ability to impact the study results.

Major protocol deviations include (but are not limited to):

- Deviation from inclusion/exclusion criteria
- Withdrawal criteria met during the study but patient was not withdrawn
- Missed evaluations
- Incorrect timing of evaluations
- Prohibited concomitant medications
- Non-compliance with IMP

Where possible; major deviations will be programmatically generated. Listings of concomitant medications will be provided to the sponsor for review to identify prohibited medications prior to database freeze.

Major protocol deviations will result in exclusion from the pharmacokinetic population if they are considered likely to affect the determination of the pharmacokinetic parameters.

9 Analysis Populations

9.1 Pharmacokinetic Population

The pharmacokinetic population will include those patients who had at least one successful blood sample taken and complete the trial without significant protocol deviations/violations which are likely to affect the determination of the pharmacokinetic parameters. This population will be used for the analysis of the primary variable.

9.2 Safety Population

The safety population is defined as all patients who receive trial medication. This population is the primary population for all safety summaries.

10 Data Reporting Conventions

10.1 Descriptive Statistics

Unless otherwise stated, all continuous parameters will be summarized using standard summary statistics as appropriate (n, mean, standard deviation [SD], coefficient of variation [%CV], minimum, median and maximum). Summary statistics for categorical variables will include frequency counts and percentages.

In the presentation of descriptive summary statistics, the minimum and maximum will be presented to the same number of decimal places as the variable being reported. The mean and median will be reported to one extra decimal place; the SD to two extra decimal places.

Frequency counts will be provided for categorical variables (e.g., gender). Unless otherwise stated, this will consist of the number of patients in a particular category and the percentage of the total number of patients per dose group, presented to one decimal place.

Analyses will be performed using the validated statistical software SAS version 9.4 or higher.

10.2 Missing Data

Data will be presented as recorded in all listings. If there are partial dates which require imputation for calculations, the day and/or month and/or year will be imputed in a conservative manner i.e. for the start dates, if only the day is missing, it will be imputed with the first day of the month and if the month is also missing, it will be imputed with the 1st January. For the end dates, if only the day is missing, it will be imputed with the last day of the month and if the month is also missing, it will be imputed with the 31st December.

No further imputations for missing data will be made.

11 Patient Disposition and Baseline Information

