11.4 Concomitant Medications

Concomitant medications recorded during the study will be coded using eMIMS. Details of concomitant medication will be listed.

Concomitant medications will be summarized according to whether they were being taken pre-study (prior medications) and/or during the study (concomitant). Prior medications are any that were being taken prior to the first dose of study medication (medication stop date prior to the first dose of study medication). Concomitant medications are any that were being taken on or after the first dose of study medication. If the start and stop dates of the concomitant medications do not clearly define the period during which a medication was taken, it will be assumed to be a concomitant medication.

Prior and concomitant medications will be summarized by treatment sequence, system class and sub-class.

12 Pharmacokinetic Assessments

The population PK analysis detailed in the protocol is not within the scope of this SAP.

Blood samples for measurement of 13-CRA and its metabolite 4-oxo-13-cis-RA will be obtained over the course of 6 hours after each dose. An additional sample 24-48 hours after day 14 will be obtained if possible.

Plasma concentrations will be expressed in ng/mL. All concentrations below the limit of quantification or missing data will be labelled as such in the concentration data listings. Concentrations below the limit of quantification will be treated as zero in summary statistics. Plasma concentrations will be listed and summarised by treatment group, day, and nominal time. In addition, individual plasma concentration-time plots, and mean plasma concentration-time plots by dose will be provided.

PK parameters will be listed. Additionally, PK parameters will be summarised by treatment group and day.

13 Safety

Safety will be assessed from records of adverse events (AEs), oro-pharyngeal tolerability, vital signs and results of physical examination.

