13.2 Adverse Events

AEs will be coded according to the latest version of the MedDRA dictionary. The severity of AEs will be coded according to the National Cancer Institute (NCI)-Common Terminology Criteria for Adverse Events (CTCAE) coding system version 4.03.

AEs will be deemed treatment emergent if they start on or after the time of the first dose of study medication.

All treatment emergent adverse events (TEAEs) and serious adverse events (SAEs) will be listed.

An overall adverse event summary will be presented for the categories: any TEAEs, any drug-related AEs, any Grade 3 or greater AEs, any Grade 3 or greater drug-related AEs, any TEAEs leading to death, any drug-related TEAEs leading to death, any serious TEAEs, any drug-related serious TEAEs, any TEAEs leading to discontinuations, and any drug-related TEAEs leading to discontinuations. Both number of events and number of patients will be tabulated. For patients, percentages will be calculated from the total number of patients per treatment.

Summaries of TEAEs and serious TEAEs will be tabulated by system organ class and preferred term sorted by decreasing frequency within system organ class (SOC). Both number of events and number of patients will be tabulated. For patients, percentages will be calculated from the total number of patients per treatment.

In addition, TEAEs and serious TEAEs will be summarized by maximum severity, system organ class and preferred term, and strongest relationship, system organ class and preferred term. If a patient experiences an adverse event more than once the event with the worst severity or at the most related to IMP occurrence will be considered. Patients will be included only once at each level where they experienced one or more events.

Oro-pharyngeal tolerability and symptoms will be separately assessed. Dry skin, peeling skin, cracked lips and dry eyes will be assessed by the investigator on a four point scale (0 = none, 1 = mild, 2 = moderate, and 3 = severe). Oro-pharyngeal symptoms will be assessed at baseline and following administration of 13-CRA during the Pharmacokinetic Day 14. Each symptom will be summarised by treatment and study day, presenting frequency counts and percentages for each value on the scale.

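### The SAP's first-of-month rule for partial start dates turns on-treatment adverse events into non-TEAEs and drops them from the TEAE tables

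*SAP*

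**What the plan says.** SAP 10.2 covers any partial date that has to be completed for a calculation. For start dates it states: "for the start dates, if only the day is missing, it will be imputed with the first day of the month". If the month is missing too, 1 January is used. The section describes this as conservative, makes no exception for adverse events, sets no floor at first dose, and closes with "No further imputations for missing data will be made".

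SAP 13.2 defines the TEAE flag: "AEs will be deemed treatment emergent if they start on or after the time of the first dose of study medication". It has no rule for partial onset dates. Tables 14.3.2.2 to 14.3.2.7 in SAP 17.1 all use this flag. Protocol 11.2 restricts the statistical report to TEAEs and leaves the criteria to the SAP.

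SAP 11.4 treats medications differently. If the dates do not place a medication clearly, "it will be assumed to be a concomitant medication".

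**The concern.** An early start date is conservative for the duration of an event. For the question of whether it began on treatment, it works the other way: it moves events to before the first dose, which is the direction of under-reporting.

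The cut-off matters because Protocol 9.1 records adverse events from consent, so pre-dose events are collected and must be separated. The same section asks for start and end dates only as far as possible, and under Protocol 4.9 patients and parents record events on diary cards. Some partial dates are therefore plausible.

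Safety and tolerability is a secondary objective, reported descriptively and mostly from the TEAE tables. SAP 5.2 captures hypercalcaemia, hepatotoxicity and triglycerides as adverse events when intervention is required, and SAP 17.1 lists no laboratory table, so the adverse event tables are their main planned summary. With at most 20 patients, each lost event is visible.

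**Working it through.** The documents give no figure on this point, so there is none to reproduce. The two rules were applied literally.

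**Example.** First dose 15 May; event starts 20 May and is recorded only as May. The imputed start is 1 May, which is before 15 May, so the event is not a TEAE. An event starting 2 June and recorded as June is imputed to 1 June and remains a TEAE.

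**Inputs.**
- Two 14-day courses and a 14-day break, which may extend to 21 days (Protocol 1.1.3).
- 14 days of follow-up (Protocol 9). The window is 14 + 14 + 14 + 14 = 56 days, or 63 with the longer break.
- Assumptions: only the day is missing; first dose is equally likely on each of 365 days; onset is uniform over the window; an imputed date equal to the first-dose date counts as on or after it.

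**Formula.** In a month of L days with first dose on day j (j > 1), every onset from day j to month end is lost: L − j + 1 days. If j = 1, none is lost. Summing over j = 2 to L gives L(L − 1)/2 per month: 465 for 31 days, 435 for 30 and 378 for 28. Over the year: 7 × 465 + 4 × 435 + 378 = 5,373 lost pairs of first-dose day and onset day.

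**Overall share lost.**
- 56-day window: 5,373 / (365 × 56) = 5,373 / 20,440 = 26.3%.
- 63-day window: 5,373 / 22,995 = 23.4%.
- Onset on the 28 dosing days only: 3,875 / 10,220 = 37.9%.

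**By day of month of first dose (56 days).** 1st: 0%. 2nd: (365 − 12)/12/56 = 52.5%. 15th: (365 − 12 × 14)/12/56 = 29.3%. 31st: 1/56 = 1.8%.

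**By phase of true onset.**

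| Phase | 14-day break | 21-day break |
|---|---|---|
| Period 1 dosing days | 3,850/5,110 = 75.3% | same |
| Break | 1,498/5,110 = 29.3% | 1,523/7,665 = 19.9% |
| Period 2 dosing days | 25/5,110 = 0.5% | 0% |
| Follow-up | 0% | 0% |

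With the 14-day break, 3,850/5,373 = 71.7% of the lost pairs lie on period 1 dosing days and 1,498/5,373 = 27.9% in the break. The loss therefore does not cancel within a patient. It evens out between formulations only as far as the two sequences are alike in size and event counts.

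**Day and month both missing.** The 1 January rule loses 18,844/20,440 = 92.2% of such events over 56 days.

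**Check of the repair.** Replacing the imputed date with the later of the first-dose date and the first of the recorded month gives 0 lost, and no imputed date contradicts the recorded month.

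**The case against.** - **Scope of 10.2.** It applies only where a calculation needs a complete date, and 13.2 does not invoke it; the SAP might then simply have no rule for these events. This is weak. Comparing a partial date with first dose is such a calculation, and only medications are given a separate default.
- **Number affected.** It is unknown and could be zero. Diary review on Day 14 (Protocol 4.10, written for oro-pharyngeal events), source checks (13.8.2) and data clarification forms (13.4) should keep it low. SAP section 16 already describes the patients' ages, so some data had been seen when it was written. This stands: the percentages are shares of an unknown count.
- **Where partial dates fall.** Period 1 dosing days are the best documented. If missing-day events occur only in the break and follow-up, the loss is 1,498/10,220 = 14.7%, or 1,523/12,775 = 11.9% with the longer break. This also stands, and lies below the 23% to 38% above.
- **Time of day.** SAP 13.2 compares with the time of first dose, and an imputed date has no time. Read as midnight, first doses on the 1st lose events too: (5,373 + 365)/20,440 = 28.1%. This raises the loss slightly.
- **What survives.** Serious events are listed regardless: "All treatment emergent adverse events (TEAEs) and serious adverse events (SAEs) will be listed". Listing 16.2.7.1 is titled for adverse events generally and may carry the event with its date as recorded ("Data will be presented as recorded in all listings"). Overall-summary rows such as "any drug-related AEs, any Grade 3 or greater AEs" are not worded as TEAEs. The 0 to 3 symptom scores are separate: "Each symptom will be summarised by treatment and study day". These points limit the harm but do not restore the event to the TEAE tables.

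**Conclusion.** The concern holds. SAP 10.2 and 13.2 together give a wrong classification: an on-treatment event dated only to the month of first dose is not a TEAE, for 353 of 365 possible first-dose dates.

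Under uniform onset, about 26% of missing-day events would be lost (23% to 38% across the main scenarios, 12% to 15% if partial dates arise only off treatment). The loss is concentrated in period 1 and the break after it. The absolute number cannot be derived from the documents and may be small.

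The effect is confined to the descriptive TEAE tables, including the serious-TEAE tables. It should be corrected because the error is silent and favours omission.

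One extension is conditional. SAP 13.2 reports events per treatment without saying how they are attributed to a formulation. If imputed onset date were used, period 2 events could also be dated before the first period 2 dose. That is not quantified here.

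**What to change.** Exempt adverse event onset dates from the general rule, in SAP 10.2 and 13.2.

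1. After a site query through the existing clarification process, class an event with a partial start date as treatment emergent unless the known part of that date, or the end date, shows that it began or ended before first dose. Footnote how many events were classed by this default.
2. Where such an event needs an imputed start, use the later of the first-dose date and the earliest date consistent with the recorded month and year.
3. Only if events are attributed to a formulation by onset date, flag those whose partial date fits either side of the first period 2 dose and show a sensitivity table.

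The cost is one or two sentences and minor programming, and the affected events can be counted directly in the database.

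The downside is that some genuinely pre-dose events would count as on-treatment. Of missing-day events that began between consent and first dose, those sharing the month of first dose are 2,219/2,555 = 87% if consent is 7 days before, 3,850/5,110 = 75% at 14 days and 5,348/10,220 = 52% at 28 days (assumed windows, uniform onset). The query or the end date may settle some of these, and the footnote shows how many events were classed by default.
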